10.2.1. Re-screening (if applicable)

Participants with uncontrolled diabetes, uncontrolled hypertension, uncontrolled thyroid disease, recent CVD event or revascularization procedure, or other medical instability due to an intervening medical condition prior to randomization, may be re-evaluated for re-screening at the investigator's discretion once remedies have been instituted and the participant is stable for at least 4 weeks (28 days) at the time of the repeat Pre-Screening Visit (Visit 0). Re-screening for medical instability may occur on a one-time basis only and should occur after a discussion with the Medical Monitor. Re-screening of participants for non-medical instability issues after 4 weeks may occur on a one-time basis after discussion with the Medical Monitor.

10.3. Retesting Visit (Visit 1.1) (if applicable)

Retesting for qualifying TG and HDL-C levels will be permissible per the guidelines described as shown Figure 4.

Retesting in cases of borderline levels of fasting TG will be permissible **on a one-time basis** if the initial value measured at Visit 1 is in the range of 175-199 mg/dL (1.98-2.25 mmol/L) or 500-650 mg/dL (5.65-7.34 mmol/L). The fasting retest value must be \geq 200 mg/dL and < 500 mg/dL for the participant to be eligible for participation in the study. Retesting for borderline levels of HDL-C will also be permissible **on a one-time basis** if the initial value measured at Visit 1 is in the range of 41-45 mg/dL (1.06-1.16 mmol/L). The fasting retest value must be \leq 40 mg/dL.

Participants do not need to qualify for both TG and HDL-C entry criteria on a single blood draw.

This visit will solely include collection of a fasting lipid sample for screening lipid levels (TG and HDL-C).

10.4. Randomization Procedures and the Randomization Visit (Visit 2)

All participants who successfully complete the Placebo Run-In Period with $\geq 75\%$ adherence to placebo tablets will be eligible for randomization to pemafibrate or placebo. The Randomization Visit (Visit 2) will involve collection of key medical, social, and anthropometric information from the participant, as well as a brief physical examination and collection of blood samples for the non-fasting lipid panel.

The following procedures will be performed at the Randomization Visit (Visit 2):

- Review inclusion and exclusion criteria and confirm eligibility
- Document complete medical history
- Document CV risk factors and alcohol use
- Review concomitant medication use
- Administer the EQ-5D-5L quality of life questionnaire
- Perform a physical examination (eg, general appearance, head and neck, chest and lungs, etc.)
- Collect vital signs (blood pressure, heart rate, body weight, waist circumference, and BMI [to be calculated])
- Perform a compliance check through unused Placebo Run-In tablet count
- Randomize participants and dispense study drug
- Collect a *non-fasting* blood sample for safety and efficacy assessments (see Appendix A in Section 21.1 for details): chemistry, hematology, lipids, and other tertiary exploratory parameters (Section 11.3)
- Collect a *non-fasting* blood sample for archiving (in countries and at sites where it is approved by the IRB/IEC/REC) and other regulatory authorities, as applicable
- Collect urine samples (for creatinine and microalbumin)
- Collect blood for serum pregnancy testing (WOCP only)
- Query participant and record any reported or observed SAEs
- Query participant and record any CV efficacy events (see Section 11.1 and Section 11.2 for definitions of efficacy events)

Randomization

The site investigator will use an interactive computer system for randomization. The randomization process will involve stratification by sex, prior history of CVD (primary vs. secondary prevention cohorts), and statin use at baseline, defined as those who are taking no statin at baseline or are statin intolerant compared to all others at the Screening/Enrollment Visit. No more than one-third of the study population will comprise participants without prior CVD (primary prevention cohort). The DSMB and Executive Committee (EC) will monitor participant profiles and may increase or restrict enrollment of certain subgroups to control this proportion.

10.5. Treatment Period Telephone Visits

In order to improve retention, provide support, and reinforce study medication dosing, a brief telephone call (Visit 3) will be conducted 2 weeks (\pm 3 days) after the Randomization Visit. Subsequent telephone visits will be conducted at 4-month intervals beginning 10 months after randomization (Month 10 visit) and continuing to the end of the study. Thus, Visits 3, 8, 10, 12, 14, 16, 18, 20, 22, 24, 26, 28, 30, 32, and 34 will be conducted by telephone. All telephone visits after Visit 3 will have a 2-week window (ie, \pm 2 weeks on either side of the scheduled visit).

During each telephone call, the following information will be gathered:

- Review concomitant medication use
- Query participant and record any reported AEs
- Query participant and record any CV efficacy events (see Section 11.1 and Section 11.2 for definitions of efficacy events)
- Instruct participants to bring all study supplies with them to the next in-person visit
- Instruct participants to fast for ≥ 8 hours immediately prior to the next in-person visit (ie, nothing by mouth, except water and essential medications)

10.6. Treatment Period In-Person Visits: 4-Month Intervals

In-person visits will continue to occur every 4 months starting at randomization (with the addition of Month 2 and Month 6 visits) and will continue until the conclusion of the study. Thus, Visits 4, 5, 6, 7, 9, 11, 13, 15, 17, 19, 21, 23, 25, 27, 29, 31, and 33 will take place in person and will have a 2-week window (ie, can take place ± 2 weeks on either side of the scheduled visit).

At the **Month 2 Visit (Fasting)**, the following procedures are to be performed:

- Review concomitant medications
- Query participant and record any reported or observed AEs
- Query participant and record any CV efficacy events (see Section 11.1 and Section 11.2 for definitions of efficacy events)
- Instruct participants to bring all study supplies with them to the next in-person visit
- Instruct participants to fast for ≥ 8 hours immediately prior to the next in-person visit (ie, nothing by mouth, except water and essential medications)
- Confirm that the participant has fasted

- Collect *fasting* blood samples for safety and efficacy assessments (see Appendix A in Section 21.1 for details): chemistry, hematology, and lipids
- Perform serum pregnancy testing (WOCP only)

Each subsequent in-person visit will involve the following procedures:

- Document CV risk factors and alcohol use
- Review concomitant medications
- Perform a physical examination (eg, general appearance, head and neck, chest and lungs, etc.)
- Collect vital signs (blood pressure, heart rate, body weight, waist circumference, and BMI [to be calculated])
- Collect unused study drug and determine study drug compliance by unused tablet count
- Dispense study drug
- Query participant and record any reported or observed AEs
- Query participant and record any CV efficacy events (see Section 11.1 and Section 11.2 for definitions of efficacy events)
- Instruct participants to bring all study supplies with them to the next in-person visit
- Instruct participants to fast for ≥ 8 hours immediately prior to the next in-person visit (ie, nothing by mouth, except water and essential medications)

At the **Month 4 Visit (Fasting)**, in addition to the in-person visit procedures listed above:

- Confirm that the participant has fasted
- Collect *fasting* blood samples for safety and efficacy assessments (see Appendix A in Section 21.1 for details): chemistry, hematology, lipids, and other tertiary exploratory parameters (Section 11.3)
- Collect a *fasting* blood sample for archiving (in countries and at sites where it is approved by the IRB/IEC/REC) and other regulatory authorities, as applicable
- Collect urine samples (for creatinine and microalbumin)
- Perform serum pregnancy testing (WOCP only)

At the **Month 6 Visit (Non-fasting)**, in addition to the in-person visit procedures listed above:

- Collect a *non-fasting* blood sample for safety and efficacy assessments (See Appendix A in Section 21.1 for details): chemistry, hematology, lipids, and other tertiary exploratory parameters (Section 11.3)
- Perform serum pregnancy testing (WOCP only)

At the Month 12 Visit (Fasting), in addition to the in-person visit procedures listed above:

- Administer the EQ-5D-5L quality of life questionnaire
- Collect *fasting* blood samples for safety and efficacy assessments (see Appendix A in Section 21.1 for details): chemistry, hematology, thyroid studies, lipids, and other tertiary exploratory parameters (Section 11.3)

At **subsequent Annual Visits (Fasting)**, in addition to the in-person visit procedures listed above:

- Confirm that the participant has fasted
- Collect *fasting* blood samples for safety and efficacy assessments (see Appendix A in Section 21.1 for details): chemistry, hematology, thyroid studies, lipids, and other tertiary exploratory parameters (Section 11.3)
- Collect urine samples (for creatinine and microalbumin)
- Perform serum pregnancy testing (WOCP only)

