10.2. Screening/Enrollment Visit (Visit 1)

A 21-day (maximum 35 day) Placebo Run-In Period will begin at Visit 1. The purpose of this Placebo Run-In Period is to ensure that participants are compliant with study medications, and are able to adhere to study procedures.

The Screening/Enrollment Visit (Visit 1) should occur within 3 weeks of the Pre-Screening Visit (Visit 0), but may be extended up to within 6 weeks of Visit 0, if needed. At this visit, clinical eligibility and exclusion criteria will be confirmed, including relevant medical history and concomitant medication use. The following procedures will be performed at the Screening/Enrollment Visit (Visit 1):

- Complete submission of medical records, if not completed at Visit 0
- Review inclusion and exclusion criteria
- Document CV risk factors and alcohol use
- Review concomitant medication use
- Perform a physical examination (eg, general appearance, head and neck, chest and lungs, etc.)
- Collect vital signs (blood pressure, heart rate, height, body weight, waist circumference, and body mass index [BMI] [to be calculated])
- Instruct participants on study drug administration
- Dispense placebo tablets for the Placebo Run-In Period
- Confirm that the participant has fasted per instructions provided during the previous visit
- Collect *fasting* blood samples for safety, eligibility, and baseline efficacy assessment (per Appendix A in Section 21.1): chemistry, hematology, thyroid studies, lipids, and other tertiary exploratory parameters (Section 11.3)
- Collect a *fasting* blood sample for archiving (in countries and at sites where it is approved by the IRB/IEC/REC) and other regulatory authorities, as applicable
- Collect serum for pregnancy testing (WOCP only)
- Query participant and record any reported or observed SAEs
- Query participant and record any CV efficacy events (see Section 11.1 and Section 11.2 for definitions of efficacy events)

- The Randomization Visit (Visit 2) should be scheduled for 21 days after the Screening/Enrollment Visit, but may be extended to 35 days if necessary
- Participants should be instructed by the site to be non-fasting for Visit 2 lab tests

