Appendix A (Section 21.1) provides a schedule of biomarker testing in the study.

Fasting Lipid Profile

A **fasting** lipid profile is obtained at the Screening/Enrollment Visit (Visit 1), Month 2 (Visit 4), Month 4 (Visit 5), Month 12 (Visit 9), annually thereafter and at the CSED Visit.

Non-Fasting Lipid Profile

A **non-fasting** lipid profile will be measured at the Randomization and Month 6 Visits.

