- 2. The change from Screening/Enrollment Visit (Visit 1) to Month 4 Visit (Visit 5) for VLDL-C (calculated). VLDL-C is calculated as TC minus HDL-C minus LDL-C, where LDL-C is measured by a direct homogenous method.
- 3. The change from Screening/Enrollment Visit (Visit 1) to Month 4 Visit (Visit 5) for ApoC3
- 4. The change from Screening/Enrollment Visit (Visit 1) to Month 4 Visit (Visit 5) for ApoE
- 5. The change from Screening/Enrollment Visit (Visit 1) to Month 4 Visit (Visit 5) for HDL-C
- 6. The change from Screening/Enrollment Visit (Visit 1) to Month 4 Visit (Visit 5) for non-HDL-C (calculated)
- 7. The change from Randomization Visit (Visit 2) to Month 6 Visit (Visit 6) for non-fasting remnant cholesterol
- 8. The change from Screening/Enrollment Visit (Visit 1) to Month 4 Visit (Visit 5) for TC
- 9. The change from Screening/Enrollment Visit (Visit 1) to Month 4 Visit (Visit 5) for ApoA1

Additional analyses will separately evaluate whether the relative effects of pemafibrate versus placebo on primary and secondary endpoints is uniform over the follow-up period. These evaluations will be based on the tests for significant interactions between study time and treatments proposed by Cox,⁶⁵ as well as consideration of trends in scaled Schoenfeld residuals in the proportional hazards model. Specifically, residuals will be plotted and a significant rank correlation of residuals with time will be indicative of a changing effect.⁷¹ In the presence of significant correlation, separate effects by time period will be reported. However, even with a significant correlation of residuals with time, the best overall estimate of the effect of treatment will be the estimate obtained from the proportional hazards model without the interaction.

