6.6.4. Visit Windows

No visit windowing will be applied to this study. For by-visit summaries, data recorded at the nominal visit will be presented. If multiple assessments occur within a visit, the result closest to the protocol defined visit will be used for the by-visit summaries.

Unscheduled measurements will not be included in by-visit summaries, but would be included in time to event analyses.

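### Section 10.6's standing fasting instruction, applied at Month 4, contradicts the non-fasting requirement at Month 6, so an unknown share of the follow-up samples for Group B endpoint 7 may be fasted

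*Protocol*

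**What the plan says.** After the Month 2 procedures, Protocol Section 10.6 opens a standing list with "Each subsequent in-person visit will involve the following procedures". One item on it is "Instruct participants to fast for ≥ 8 hours immediately prior to the next in-person visit". The Month 4 procedures are then given "in addition to the in-person visit procedures listed above", so they add to the standing list and do not replace it.

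The same section lists Visits 4, 5, 6 and 7 as consecutive in-person visits. Visit 5 is Month 4 and Visit 6 is Month 6. The Month 6 block is headed "Month 6 Visit (Non-fasting" and calls for a non-fasting sample. Other places agree:

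- Table 4 ticks the non-fasting sample row at Visit 6, and footnote d gives that draw as the reason for an in-person visit.
- Section 11.3 says that a non-fasting "lipid profile will be measured at the Randomization and Month 6 Visits".
- Appendix A codes Visit 6 as N.

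For the other non-fasting visit, Section 10.2 is explicit: "Participants should be instructed by the site to be non-fasting for Visit 2 lab tests".

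The endpoint that depends on Month 6 is number 7 in Group B (Protocol Section 14.5): "The change from Randomization Visit (Visit 2) to Month 6 Visit (Visit 6) for non-fasting remnant cholesterol". SAP Section 3.2.2.2 defines it as a percent change between the same two visits.

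**The concern.** Endpoint 7 asks what pemafibrate does to remnant cholesterol in the non-fasting state. That needs both samples, Visit 2 and Month 6, to be taken in that state. The plan secures this at Visit 2 with a direct instruction. For Month 6, the only instruction that it puts in front of participants says the opposite.

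If some Month 6 samples are fasted, change within each arm mixes the drug effect with the effect of fasting, and the between-arm difference no longer describes a purely non-fasting quantity. Three other uses of Month 6 data are exposed:

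- The SAP Section 8.3 on-treatment subgroups for non-fasting TG and non-fasting remnant cholesterol, both cut at Month 6 medians.
- Group B endpoints 8 and 9 (TC and ApoA1), which can be tested only if endpoint 7 succeeds.
- The TG alerts in Protocol Section 8.2.3, which have separate fasting and non-fasting criteria. Which one applies at Month 6 depends on the participant's actual state, so those passages need to be consistent with Section 10.6.

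**Working it through.** No sample size, power or alpha figure is in question, so there is no stated figure to reproduce. The check is a trace of the visit sequence in Sections 10.5 and 10.6 against the fasting codes in Appendix A.

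| Visit at which the instruction is given | Next in-person visit | Required state there | Result of telling the participant to fast |
|---|---|---|---|
| V4 (Month 2) | V5 (Month 4) | Fasting (F) | Consistent |
| V5 (Month 4) | V6 (Month 6) | Non-fasting (N) | Contradiction |
| V6 (Month 6) | V7 (Month 8) | Not in Appendix A | No effect on a scheduled sample |
| V7 (Month 8) | V9 (Month 12) | Fasting (F) | Consistent |
| V9 (Month 12) | V11 (Month 16) | Either (R) | No contradiction |
| V11 onward | Visits coded R or F | Either, or fasting | No contradiction |

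Month 4 to Month 6 is the only step at which the standing instruction conflicts with the required state.

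**Could a later contact correct it?** Section 10.5 schedules a telephone visit at Week 2 (Visit 3) and the next at Month 10 (Visit 8). None falls between Month 4 and Month 6.

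**Does the analysis plan catch it?** SAP Section 8.5 analyses Group B by ANCOVA on percent change, with baseline, treatment and the randomisation strata. Fasting status is not a term, and no rule covers a sample taken in the wrong state. SAP Section 10.5 splits results by fasting status, but only for triglycerides and glucose in the laboratory summaries.

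**Illustration of size (assumptions only).** Let f be the share of Month 6 samples that are fasted and d the fraction by which fasting lowers remnant cholesterol. Suppose that fasting multiplies the Month 6 value by the same factor in both arms. The mean factor is then 1 − f×d, and the between-arm difference in percent change shrinks by the relative amount f×d. Neither f, d nor the true effect is in the documents.

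- Take f = 50%, d = 20%, no true change on placebo and a true fall of 40% on pemafibrate. The factor is 1 − 0.50×0.20 = 0.90.
- Placebo: 1.00×0.90 = 0.90, a 10% fall.
- Pemafibrate: 0.60×0.90 = 0.54, a 46% fall.
- Difference: 46 − 10 = 36 points instead of 40.
- Range: f = 25% and d = 10% give a relative shrinkage of 0.25×0.10 = 2.5%; f = 90% and d = 30% give 0.90×0.30 = 27%.

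Under an additive model, in which fasting takes the same 10 points off each arm, the falls are 10 and 50 and the difference stays at 40. The attenuation therefore depends on the model as well as on f and d.

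**The case against.** A reader might infer that Month 6 would be measured largely in fasted people. The documents do not support that. Several specific passages tell sites that Month 6 is non-fasting, and a site that collects a fasted sample departs from the plan as much as one that skips the generic fasting line. Sites receive both messages, and nothing shows which prevails; the fasted share could lie anywhere from 0 to 100%.

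The missing check at Month 6 is also weak evidence alone. Visit 2 has no step to confirm a non-fasting state, Month 12 has no step to confirm fasting, and the Month 12 list omits urine and pregnancy tests that Table 4 schedules. Section 10.6 is an incomplete checklist. The argument rests on an instruction that is present and contrary, not on one that is absent.

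It is tempting to cite SAP Section 6.6.4, "For by-visit summaries, data recorded at the nominal visit will be presented", as proof that fasted samples enter endpoint 7 as non-fasting. That sentence governs by-visit summaries, not the Group B ANCOVA. The sound statement is that the SAP has no rule for the case.

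A reader might also infer bias between arms. Participants in both arms get the same instruction in a double-blind trial, so no direct bias is shown. Endpoint 7 is seventh in a group tested at alpha 0.001, and only after the primary endpoint and six earlier lipid endpoints succeed. This limits the consequence but does not remove the contradiction.

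**Conclusion.** The contradiction is certain and can be read directly from Section 10.6. Its consequence is not quantifiable: an unknown share of Month 6 samples may be fasted, and to that extent endpoint 7 sets a non-fasting baseline against a partly fasted follow-up. The threat is to the interpretation and size of that estimate, and to the two Month 6 non-fasting subgroups. It is not clearly a threat to the validity of the randomised test. The primary endpoint and the Group A clinical endpoints do not use these samples. The drop from 40 to 36 points is an illustration under a multiplicative model with assumed inputs, not an estimate for this trial. The point is worth correcting because the plan's own rule can yield the wrong sample state for a named secondary endpoint and the correction is cheap.

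**What to change.** **Protocol.** Reconcile Section 10.6 with Table 4 and Appendix A. Except the Month 4 visit from the fasting line, and put in its place an instruction to be non-fasting for Month 6, matching what Section 10.2 does for Visit 2. At Month 6, add a check and a record of fasting status. The cost is a line or two of text and a site memo; no visit or sample is added. Protocol Version 3 already reports an actual enrolment period of 3.0 years, so the memo may reach few remaining Month 6 visits.

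**SAP.** Where fasting status is recorded, add a sensitivity analysis of Group B endpoint 7 that excludes, or reports separately, samples taken in the fasted state at Visit 2 or Month 6. Apply the same split to the Month 6 non-fasting subgroups. This step also helps for visits already completed. The documents do not show that status is recorded for the Month 6 remnant cholesterol sample; the split in SAP Section 10.5 suggests that it may be, and this should be confirmed first. The downside is fewer evaluable samples. Selection on Month 6 status is also post-randomisation, so counts of fasted and unknown samples should be shown by arm and the full ITT analysis should remain the main one.

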10.7. Common Study End Date (CSED) Visit

Study close out will begin after 1,304 adjudicated and confirmed primary endpoint events have accrued, with a minimum of 200 events in women. The estimated total study duration will be approximately 5 years. The CSED Visit will be scheduled within a 60-day window after the study termination is announced, irrespective of the date that the participant was randomized.

The CSED Visit is required for all participants. During scheduling of this visit, participants will be instructed to fast for ≥ 8 hours immediately prior to this visit (ie, nothing by mouth, except water and essential medications).

In the rare case that the CSED Visit cannot occur within the 60-day timeframe following the study termination, attempts to contact the participant must be recorded on a special contact form, until/unless appropriate information is obtained. The following procedures will be performed at the CSED Visit:

- Document CV risk factors and alcohol use
- Review concomitant medication use

- Administer the EQ-5D-5L quality of life questionnaire
- Perform a physical examination (eg, general appearance, head and neck, chest and lungs, etc.)
- Collect vital signs (blood pressure, heart rate, body weight, height, waist circumference, and BMI [to be calculated])
- Collect unused study drug and determine study drug compliance by unused tablet count
- Query participant and record any reported or observed AEs
- Query participant and record any CV efficacy events (see Section 11.1 and Section 11.2 for definitions of efficacy events)
- Collect *fasting* blood samples for safety and efficacy assessments (see Appendix A in Section 21.1 for details): chemistry, hematology, thyroid studies, lipids, and other tertiary exploratory parameters (Section 11.3)
- Collect urine samples (for creatinine and microalbumin)
- Collect serum for pregnancy testing (WOCP only)

The CSED Visit will be followed 30 days later by a Post-Study Safety telephone call to collect any final AEs unless the participant had interrupted or discontinued study drug greater than 30 days before the CSED Visit.

